8.1. Study Subjects

8.1.1. Disposition of Subjects

Subjects disposition will be summarized, including the number of subjects enrolled, attempted implant, implanted, died, withdrawn, lost-to follow up, and completed each scheduled follow up visit during the study.

Clinical Investigation Plan (CIP) Deviations 8.1.2.

Protocol deviations will be reported regardless of whether medically justifiable, pre-approved by Medtronic, or taken to protect the subject in an emergency. CIP deviations will be summarized by follow up visit.

8.1.3. Analysis Sets

Within the enrolled population (subjects who signed consent form) the following analysis sets are distinguished:

- The attempted implant set: The attempted implant set consists of all enrolled subjects with an attempted TAVR implant procedure, defined as when the subject is brought into the procedure room and any of the following have occurred: anesthesia or conscious sedation administered, vascular line placed, TEE placed, or any monitoring line placed. Subjects will be analyzed according to their first attempted procedure. Enrolled subjects that do not receive an attempted TAVR implant are to be exited from the study. Time zero begins on the date of first attempted implant procedure.
- The implanted (IMP) set: The implanted set consists of all the attempted implant subjects who are actually implanted with the Medtronic TAV device. Subjects with an

Version 5.0

Page 13 of 21

attempted implant that do not actually receive a TAV are to be exited from the study following discharge from the index hospitalization. Time zero begins on the date of first attempted implant procedure.

- Per-protocol (PP) set 1 for TAVR care pathway: This per-protocol set 1 consists of all implanted subjects with percutaneous and transfemoral access only and no concomitant procedures including percutaneous coronary intervention (PCI). This per-protocol set 1 will be used for the secondary endpoint median days from index procedure to discharge. Time zero begins on the date of first attempted implant procedure.
- Per-protocol (PP) set 2 for conduction disturbance pathway: This per-protocol set 2 consists of all attempted implant subjects whose peri- and post-TAVR index procedure follows the conduction disturbance pathway management and cusp overlap technique. The cusp overlap technique followed can be defined as the 4 essential COT steps followed, which means the MUO case evaluation step 1, step 2 and/or 3, step 5 and step 15 are each followed. This per-protocol set 2 will be used for the secondary endpoint rate of pacemaker implant for new onset or worsening conduction disturbance at 30 days.
- **Roll-in:** Roll-in subjects will not be analyzed with the study cohort attempted implant, implanted, or per protocol sets and will be analyzed separately using descriptive statistics.

Index Procedure 8.1.4.

Index procedure is defined as the first procedure that the Medtronic EnVeo™ PRO Delivery Catheter System or Evolut™ PRO+ Delivery Catheter System is introduced.

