8.2. General Methodology

Descriptive statistics will be used to report study data.

For continuous variables (e.g., age), the mean, median, standard deviation, minimum, maximum, and first and third quartiles will be presented. For categorical variables, the number and percentage of subjects in the category of interest will be presented.

For time to event variables, Kaplan-Meier analyses of event or event-free rates at 1 and 12 months will be presented. For these analyses, the time points will correspond to 30 days and 365 days post-implantation, respectively. At each time point with data, the product limit estimate of the event or event-free rates will be presented. In addition, 95% confidence interval using the Greenwood standard error will be presented. For subjects without an event, the date of censoring will be the latest date of all follow-up visits, assessments, and events (for nondeath events).

Version 5.0

Page 14 of 21

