8.8.2. Secondary Endpoint #1

Median days from index procedure to discharge.

Hypothesis/Decision criteria:

No specific hypotheses or pass/fail criteria have been set. The analysis will be descriptive, and no statistical hypothesis test will be performed.

Endpoint Definition/Parameters to Be Estimated:

Days from index procedure to discharge will be summarized.

Data Collection and Analysis Dataset:

Data will be collected on a Procedure (PROC) and/or Discharge (DISC) CRF. This objective will be analyzed for the attempted implant set, per-protocol (PP) set 1 for TAVR care pathway cohort, and per-protocol (PP) set 2 for Conduction Disturbance pathway.

Version 5.0

Page 16 of 21

Analysis Method:

Descriptive statistics will be provided. The mean, median, standard deviation, minimum, maximum, and first and third quartiles will be presented.

Secondary Endpoint #2 8.8.3.

Percentage of subjects with \geq moderate agric regurgitation (AR) at discharge.

Hypothesis/Decision criteria:

No specific hypotheses or pass/fail criteria have been set. The analysis will be descriptive, and no statistical hypothesis test will be performed.

Endpoint Definition/Parameters to Be Estimated:

Aortic valve function will be based on core lab echocardiographic recordings. The parameter to be estimated is the grade of aortic valve regurgitation using echo, in subjects at discharge.

Data Collection and Analysis Dataset:

Data will be collected on Core lab ECHOCARDIOGRAM CRF. This objective will be analyzed for both the implanted (IMP) set, per-protocol (PP) set 1 for TAVR care pathway cohort, and perprotocol (PP) set 2 for Conduction Disturbance pathway. In addition, AR data will be summarized at each follow up visit.

Analysis Method:

AR will be presented with frequencies and percentages at screening, discharge and 1-year post procedure.

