9.5. Statistical Methods

Refer to Section 8 for details on the statistical analysis for the Optimize PRO study. The roll-in analysis set will not be applicable for the FX Addendum. The analysis will be descriptive, and no statistical hypothesis tests will be performed.

Version 5.0

Page 20 of 21

The attempted implant set, implanted set, PP set 1 for TAVR care pathway, and PP set 2 for conduction disturbance pathway will be defined the same for subjects enrolled in the FX Addendum.

The primary analysis cohort for the primary endpoint and secondary safety and effectiveness endpoints will be the attempted implant set. Secondary and additional exploratory endpoints will be analyzed for both the attempted implant set, per protocol (PP) set 1 for TAVR care pathway cohort, and per protocol (PP) set 2 for Conduction Disturbance pathway. However, Percentage of subjects with an NCC depth of implant between 1.0 and 5.0 mm, Percentage of subjects with an absolute canting value |NCC-LCC| of ≤ 2.0 mm, Percentage of subjects in which the target depth of implant was achieved, and Echocardiography data will be analyzed based on the implanted set.

All post-reintervention echocardiographic data will be excluded from hemodynamic analyses unless specified otherwise. Echocardiographic assessments after the first reintervention date will be excluded from any analyses using echo data. Reinterventions will be based on CEC adjudication.

Changes to Planned Analysis 10.

The planned analyses in this SAP are aligned with the planned analyses noted in the CIP (6.0, 04 May 2021). Additionally, all analyses defined for the FX Addendum are consistent with the version of the Addendum for which this plan was developed (3.0, 15 December 2022).

11. **Validation Requirements**

Level 1 validation (independent validation) will be used for the analysis datasets and the primary and secondary endpoints. Level 2 validation (peer review) will be used for additional analyses, data summaries, and listings.

References 12.

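### Do the outdated catheter list in SAP 8.1.4 and the post-implantation wording in SAP 8.2 leave the FX Addendum without a clear time zero?

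*SAP*

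**What the plan says.** SAP 9.5 sends the FX analysis back to the parent methods ("Refer to Section 8 for details on the statistical analysis for the Optimize PRO study") and says the four analysis sets "will be defined the same for subjects enrolled in the FX Addendum". Section 9 gives no definition of the index procedure for FX.

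Four places in Section 8 bear on the clock:

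- **8.1.3 (Analysis Sets).** For the attempted implant set, the implanted set and per-protocol set 1: "Time zero begins on the date of first attempted implant procedure". The attempted implant bullet adds that subjects are analysed by their first attempted procedure. The bullet for per-protocol set 2 names its endpoint ("This per-protocol set 2 will be used for the secondary endpoint rate of pacemaker implant for new onset or worsening conduction disturbance") but has no time-zero sentence.
- **8.1.4 (Index Procedure).** The definition reads: "Index procedure is defined as the first procedure that the Medtronic EnVeo™ PRO Delivery Catheter System or Evolut™ PRO+ Delivery Catheter System is introduced". No FX catheter is listed there.
- **8.2 (General Methodology).** For Kaplan-Meier estimates, "the time points will correspond to 30 days and 365 days post-implantation, respectively".
- **8.8.2 (Secondary Endpoint #1).** "Days from index procedure to discharge will be summarized".

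On the cohort, SAP 9.5 says: "The primary analysis cohort for the primary endpoint and secondary safety and effectiveness endpoints will be the attempted implant set". Protocol 7.1.1 and 7.1.2.2 identify the catheter as the Evolut FX delivery system. Protocol 10.1.3.1 sets Day 0 at the index procedure.

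**The concern.** Read literally, no FX subject meets SAP 8.1.4, because neither named catheter is used in the addendum. Yet the term it defines appears in the name of a secondary endpoint, in the membership rule for per-protocol set 2 and in Day 0.

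SAP 8.2 appears to contradict SAP 8.1.3. It also cannot be applied to a subject who is attempted but receives no valve, and such subjects belong to the primary cohort. Per-protocol set 2, the set named for the 30-day pacemaker endpoint, appears to have no origin at all.

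The origin decides whether a death, stroke or pacemaker falls within 30 days, and where days to discharge begin. If two analysts followed different sentences, they could report different figures for the same atypical subject.

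**Working it through.** **Step 1. Which origin does each FX endpoint have?**

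| Endpoint | Text that sets the clock | Origin |
|---|---|---|
| Death or stroke, 30 days | 8.1.3 through 9.5; 8.8.1 counts from the procedure | First attempt |
| Days to discharge | 8.1.3; the per-protocol set 1 bullet names this endpoint and then states time zero, as does Protocol 13.1.1 | First attempt |
| Pacemaker, 30 days | 8.1.3; 8.8.4 counts from the procedure | First attempt |
| Readmission; 1-year composite | 8.1.3; 8.8.5 and 8.8.6 count from the procedure | First attempt |

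SAP 8.6 and Protocol 13.3 also count from the procedure. The reference to implantation in 8.2 is one general sentence that translates 1 and 12 months into 30 and 365 days. The set-specific and endpoint-specific texts outweigh it.

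Per-protocol set 2 is drawn from the attempted implant subjects. Each member already has a time zero as a member of that set, and no passage assigns another. This is an omission, not a conflict.

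**Step 2. When can the origins differ?** All are calendar dates. If first attempt, catheter introduction and implant share a day, every estimate is identical. They differ, or one is missing, only when no catheter is introduced, no valve is implanted, or the implant falls on a later day. SAP 8.1.3 and Protocol 13.1.1 also exit non-implanted subjects after discharge from the index hospitalization, which limits staged cases further.

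**Step 3. How large could the effect be?** The documents give no count of such subjects, so the inputs below are assumptions.

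*Reclassification.* N = 150 (SAP 9.4); share with differing dates d = 1% to 5%; 30-day event risk p = 2% to 4%; every such event assumed to change classification, which is an upper bound.

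- Expected subjects moved, N·d·p: 150 × 0.01 × 0.02 = 0.03, up to 150 × 0.05 × 0.04 = 0.30.
- Mean shift, 100·d·p: 0.02 to 0.20 points.
- Chance that at least one moves, 1 − (1 − d·p)^150: 3.0% to 25.9%.
- One subject: 1/150 = 0.67 points. For scale, exact 95% intervals are 0.4% to 5.7% for 3/150 and 1.5% to 8.5% for 6/150.

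*Dropping non-implanted subjects.* This is what counting strictly from implantation would do. Compare e/150 with (e − d)/(150 − k), where e is the number of events, k the number of subjects without an implant and d (here a count) the events among them.

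| e | k | d | From attempt | From implant |
|---|---|---|---|---|
| 5 | 1 | 1 | 5/150 = 3.33% | 4/149 = 2.68% |
| 5 | 2 | 2 | 5/150 = 3.33% | 3/148 = 2.03% |
| 5 | 5 | 0 | 5/150 = 3.33% | 5/145 = 3.45% |
| 3 | 2 | 2 | 3/150 = 2.00% | 1/148 = 0.68% |
| 8 | 8 | 0 | 8/150 = 5.33% | 8/142 = 5.63% |

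Over e = 3 to 8, k = 1 to 8 and d = 0 to 2, the change runs from about −1.3 to +0.3 points. To get it, an analyst would have to remove subjects whom SAP 9.5 places in the primary cohort.

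*Median days to discharge.* Take an assumed distribution of 90, 30, 15, 9 and 6 subjects at 1, 2, 3, 4 and 6 days. Adding 2 days to 1, 3 or 8 of the shortest stays leaves the median at 1.0. With 15 subjects (10% of 150) it becomes 1.5.

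**The case for a change.** The best argument for a change has four parts.

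- **An attempt and an index procedure are different events.** Under SAP 8.1.3 an attempt needs only sedation or a line placed in the procedure room. Under 8.1.4 an index procedure needs a catheter introduced. Adding the FX catheter to the list would therefore still leave a subject aborted before catheter introduction with a time zero but no index date.
- **Two people will program this.** SAP 11 requires independent validation of the analysis datasets and of the primary and secondary endpoints, so two programmers may work from the differing sentences.
- **The effect can exceed the average shift.** If non-implanted subjects had several of the few events, the primary rate could move by more than a point.
- **The remedy is cheap.** One sentence in Section 9 would do.

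The inconsistency of wording stands: 8.1.4 was not updated and 8.2 is loosely phrased. The rest does not lead to a different analysis. For the subject aborted before catheter introduction, the 8.1.3 rule of analysis by first attempted procedure supplies the date. Two programmers working independently would both have 8.1.3 and the endpoint sections, and a mismatch is what validation is meant to expose before reporting. The shift of more than a point arises only by departing from the cohort stated in 9.5. Low cost shows that an edit would be harmless, not that it would alter a result.

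Whether Day 0 needs attention cannot be judged. The addendum defers to a parent protocol that is not among the documents and may define the term.

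**Conclusion.** The concern is right about the text but calls for no change. The catheter list in SAP 8.1.4 is a leftover from the parent study, the mention of implantation in 8.2 is loose general wording, and the missing sentence for per-protocol set 2 is filled by its being a subset of the attempted implant set. An analyst following SAP 8.1.3, 8.8 and 9.5 starts every FX clock at the first attempted implant procedure.

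The effect is nil for same-day procedures. For the others it is probably nil and cannot be quantified from the documents: the average shift of 0.02 to 0.20 points rests wholly on the assumed 1% to 5% share and 2% to 4% risk. The study is descriptive, so no error rate or sample size depends on the point. Aligning the three sentences at some later revision would be housekeeping.

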8.2. General Methodology

Descriptive statistics will be used to report study data.

For continuous variables (e.g., age), the mean, median, standard deviation, minimum, maximum, and first and third quartiles will be presented. For categorical variables, the number and percentage of subjects in the category of interest will be presented.

For time to event variables, Kaplan-Meier analyses of event or event-free rates at 1 and 12 months will be presented. For these analyses, the time points will correspond to 30 days and 365 days post-implantation, respectively. At each time point with data, the product limit estimate of the event or event-free rates will be presented. In addition, 95% confidence interval using the Greenwood standard error will be presented. For subjects without an event, the date of censoring will be the latest date of all follow-up visits, assessments, and events (for nondeath events).

Version 5.0

Page 14 of 21

8.3. Missing Data

Every effort will be undertaken to minimize missing data. However, some missing data is inevitable, and the trial is designed with the expectation that there may be up to 6% of primary data missing at 12 months. Unless otherwise specified, no statistical techniques will be used to impute missing data. The number of subjects included in each analysis will be reported so that the reader can assess the potential impact of missing data.

In the case of partial dates, if only the month and year are known, the event or assessment will be analyzed as if it occurred on the 15th of that month. If only the year is known, the event or assessment will be analyzed as if it occurred on June 30th of that year. These resolutions of partial dates are subject to the restrictions that events must occur no earlier than the procedure date.

8.4. Demographic and Other Baseline Characteristics

Demographic and baseline characteristics will be summarized for the attempted implant analysis set. Continuous variables will be summarized with means, medians, standard deviations, minimums, maximums, and first and third quartiles. Categorical variables will be summarized with frequencies and percentages.

8.5. Treatment Characteristics

Procedure data will be summarized for the attempted implant analysis set. Continuous variables will be summarized with means, medians, standard deviations, minimums, maximums, and first and third quartiles. Categorical variables will be summarized with frequencies and percentages.

8.6. Interim Analyses

The first interim analysis will be conducted after 100 subjects are enrolled in the study cohort attempted implant set and followed through 30 days post procedure.

As this is not a hypothesis driven study, additional interim analyses may occur as deemed necessary.

8.7. Echocardiographic Assessments After Reintervention

All post-reintervention echocardiographic data will be excluded from hemodynamic analyses unless specified otherwise. Echocardiographic assessments after the first reintervention date will be excluded from any analyses using echo data. Reinterventions will be based on CEC adjudication.

Version 5.0

Page 15 of 21

Medtronic

8.8. Evaluation of Endpoints

8.8.1. **Primary Endpoint**

The primary endpoint is the rate of all-cause mortality or all-stroke at 30 days.

Hypothesis/Decision criteria:

No specific hypotheses or pass/fail criteria have been set. The analysis will be descriptive, and no statistical hypothesis test will be performed.

Endpoint Definition/Parameters to Be Estimated:

All-cause mortality or all-stroke event rate estimate will be provided at 30 days post procedure.

Data Collection and Analysis Dataset:

Data will be collected on a CEC CRF. This objective will be analyzed for both the attempted implant set, per-protocol (PP) set 1 for TAVR care pathway cohort, and per-protocol (PP) set 2 for Conduction Disturbance pathway.

Analysis Method:

A Kaplan-Meier analysis will be performed.

8.8.2. Secondary Endpoint #1

Median days from index procedure to discharge.

Hypothesis/Decision criteria:

No specific hypotheses or pass/fail criteria have been set. The analysis will be descriptive, and no statistical hypothesis test will be performed.

Endpoint Definition/Parameters to Be Estimated:

Days from index procedure to discharge will be summarized.

Data Collection and Analysis Dataset:

Data will be collected on a Procedure (PROC) and/or Discharge (DISC) CRF. This objective will be analyzed for the attempted implant set, per-protocol (PP) set 1 for TAVR care pathway cohort, and per-protocol (PP) set 2 for Conduction Disturbance pathway.

Version 5.0

Page 16 of 21

Analysis Method:

Descriptive statistics will be provided. The mean, median, standard deviation, minimum, maximum, and first and third quartiles will be presented.

Secondary Endpoint #2 8.8.3.

Percentage of subjects with \geq moderate agric regurgitation (AR) at discharge.

Hypothesis/Decision criteria:

No specific hypotheses or pass/fail criteria have been set. The analysis will be descriptive, and no statistical hypothesis test will be performed.

Endpoint Definition/Parameters to Be Estimated:

Aortic valve function will be based on core lab echocardiographic recordings. The parameter to be estimated is the grade of aortic valve regurgitation using echo, in subjects at discharge.

Data Collection and Analysis Dataset:

Data will be collected on Core lab ECHOCARDIOGRAM CRF. This objective will be analyzed for both the implanted (IMP) set, per-protocol (PP) set 1 for TAVR care pathway cohort, and perprotocol (PP) set 2 for Conduction Disturbance pathway. In addition, AR data will be summarized at each follow up visit.

Analysis Method:

AR will be presented with frequencies and percentages at screening, discharge and 1-year post procedure.

8.8.4. Secondary Endpoint #3

Rate of pacemaker implant for new onset or worsening conduction disturbance at 30 days.

Hypothesis/Decision criteria:

No specific hypotheses or pass/fail criteria have been set. The analysis will be descriptive, and no statistical hypothesis test will be performed.

Endpoint Definition/Parameters to Be Estimated:

Pacemaker implant for new onset or worsening conduction disturbance event rate estimate will be provided at 30 days post-procedure.

Version 5.0

Page 17 of 21

Data Collection and Analysis Dataset:

Data will be collected on a Permanent Pacemaker Implant CRF. This endpoint will be analyzed for both the attempted implant set and per-protocol (PP) set 2 for Conduction Disturbance pathway.

Analysis Method:

A Kaplan-Meier analysis will be performed. The overall rate of permanent pacemaker implantation at 30 days will be provided. The rates of permanent pacemaker implantation at 30 days by region (US/CAN, EMEA, and ANZ) centers will be provided and compared.

8.8.5. Additional Exploratory Endpoint #1

30-day and 1-year hospital re-admission rates.

Hypothesis/Decision criteria:

No specific hypotheses or pass/fail criteria have been set. The analysis will be descriptive, and no statistical hypothesis test will be performed.

Endpoint Definition/Parameters to Be Estimated:

Rehospitalization event rate estimate will be provided at 30 days and 12 months postprocedure.

Data Collection and Analysis Dataset:

Data will be collected on a Rehospitalization (REHOSP) CRF. This endpoint will be analyzed for both the attempted implant set, per-protocol (PP) set 1 for TAVR care pathway cohort, and perprotocol (PP) set 2 for Conduction Disturbance pathway.

Analysis Method:

A Kaplan-Meier analysis will be performed.

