8.9. Safety Evaluation

Primary and secondary safety endpoints will be summarized as noted in Section 8.7 of this SAP. Adverse events will be provided in a listing and summarized.

The below 3 listings will be provided for the attempted implant set:

- A listing of deaths and reasons for deaths.
- A listing of adverse events with AE start and end dates, severity, outcomes, and procedure/device relatedness.
- A listing of device deficiencies.

9. Analysis for FX Addendum

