9.3.3. Additional Exploratory Endpoints

The following are additional exploratory endpoints:

- 30-day and 1-year hospital re-admission rates
- 1-year composite of all-cause mortality or all-stroke
- Percent of patients with a major vascular complication
- Percent of patients that require a recapture or resheath of the TAV
- Percent of patients in which the target depth of implant was achieved
- Orientation of valve relative to native anatomy

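### One-year readmission is estimated by Kaplan-Meier with death implicitly censored, so the reported rate will equal or modestly exceed the share of subjects readmitted

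*SAP*

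**What the plan says.** The FX Addendum lists "30-day and 1-year hospital re-admission rates" among its exploratory endpoints (SAP 9.3.3; protocol 5.2.3 and 13.6). For methods, SAP 9.5 points back: "Refer to Section 8 for details on the statistical analysis for the Optimize PRO study".

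In Section 8, SAP 8.8.5 defines the parameter: "Rehospitalization event rate estimate will be provided at 30 days and 12 months postprocedure". The analysis method is one sentence: "A Kaplan-Meier analysis will be performed". Death is not a component of this endpoint, unlike the composite in SAP 8.8.6.

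SAP 8.2 sets the rules for all time-to-event variables. The product-limit estimate is reported at 30 and 365 days. On the interval: "In addition, 95% confidence interval using the Greenwood standard error will be presented". On censoring: "For subjects without an event, the date of censoring will be the latest date of all follow-up visits, assessments, and events (for nondeath events" (the sentence ends there with a closing bracket). No rule is given for a subject who dies before a non-fatal event, and no competing-risk method appears in the protocol addendum or the SAP. The governing parent protocol is not among the documents, but SAP Section 10 states that the SAP is aligned with it.

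Deaths are visible elsewhere: SAP 8.1.1 counts them in disposition, and SAP 8.9 provides "A listing of deaths and reasons for deaths".

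**The concern.** A subject who has died cannot be readmitted. Kaplan-Meier with death censored treats that subject as if readmission were still possible, at the same hazard as those still alive. It therefore estimates the readmission risk in a hypothetical population in which nobody dies first. Most readers will take a one-year readmission rate to mean the proportion of treated subjects who came back to hospital within the year. The two agree only if no death before readmission affects the risk set; otherwise the Kaplan-Meier figure is the higher.

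The endpoint is descriptive, so the printed estimate and its interval are the whole result. A gap in one direction that does not shrink with sample size matters more there than it would beside a formal comparison. The Greenwood interval is centred on the same quantity and does not account for the gap.

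**Working it through.** **Is death censored?** The SAP does not say so in words. It follows from SAP 8.2: a subject who dies without a readmission is without an event, so a censoring date applies. Whether the bracketed phrase about non-death events puts that date at death or at the last earlier contact, the subject leaves the risk set. The direction is the same on either reading.

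**Inputs.** The plan states no readmission rate, mortality rate or precision, so there is no figure of its own to reproduce. Let R be the one-year cumulative incidence of readmission and D the share dying before any readmission. Both are assumed: R from 15% to 40%, D from 1% to 10%. The sample size of 150 is from SAP 9.4.

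**Closed form, constant cause-specific hazards.** The total hazard over the year is L = -ln(1 - R - D). The readmission hazard is h = L × R/(R + D). Kaplan-Meier with death censored estimates 1 - exp(-h).

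For R = 30%, D = 5%: L = -ln(0.65) = 0.4308; h = 0.4308 × 0.30/0.35 = 0.3692; 1 - exp(-0.3692) = 30.87%.

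| R | D | 1-KM | Excess (points) |
|---|---|---|---|
| 15% | 1% | 15.08% | 0.08 |
| 15% | 10% | 15.85% | 0.85 |
| 20% | 5% | 20.56% | 0.56 |
| 30% | 1% | 30.17% | 0.17 |
| 30% | 5% | 30.87% | 0.87 |
| 30% | 8% | 31.44% | 1.44 |
| 40% | 5% | 41.22% | 1.22 |
| 40% | 10% | 42.57% | 2.57 |

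**Timing of deaths.** If all such deaths came before any readmission, 1-KM would reach R/(1 - D): 0.30/0.95 = 31.6%, or 0.40/0.90 = 44.4%, an excess of 4.4 points. If they all came after the last readmission, the excess would be zero. The constant-hazard values lie between these limits.

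**Separating death from loss to follow-up.** Kaplan-Meier properly corrects for ordinary dropout, so the fair comparison is with the Aalen-Johansen cumulative incidence in the same data, not with the crude proportion. SAP 8.3 expects that "there may be up to 6% of primary data missing at 12 months"; this is used here as a 6% dropout rate. In simulations of 150 subjects (4,000 runs), the mean of 1-KM minus Aalen-Johansen was:

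- R 15%, D 1%: 0.08 points
- R 30%, D 5%: 0.88 points (95% of runs 0.25 to 1.70)
- R 30%, D 8%: 1.45 points (0.61 to 2.53)
- R 40%, D 10%: 2.56 points (1.22 to 4.23)

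The Aalen-Johansen means were within 0.06 points of the true R. In a separate set of 12 scenarios (150 and 650 subjects, R = 25%, 1,000 runs each), 1-KM was never below the cumulative incidence.

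**Against sampling error.** The approximate 95% half-width is 1.96 × sqrt(R(1 - R)/150): 5.7, 6.4, 7.3 and 7.8 points for R = 15, 20, 30 and 40%.

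**At 30 days.** With R from 5% to 20% and D from 0.5% to 3%, the same formula gives an excess of 0.01 to 0.33 points. This covers 30-day readmission and 30-day pacemaker implant; neither needs a change.

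**The case against.** The strongest reply is that Kaplan-Meier with death censored is a definite, prespecified quantity. It is wrong only if read as the share readmitted, so the complaint is an unstated target and not a mistake. The first part is fair. But the SAP nowhere says it wants a risk with death removed, and a readmission rate will not be read that way.

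The second reply is size. Every input is assumed, and the 2.6-point figure needs high readmission and high mortality together. The exclusions in protocol 9.4 (short non-cardiac life expectancy, low ejection fraction, multiple frailty markers) should limit early deaths. At 30% and 5% the excess is 0.87 points, or about 1.3 subjects in 150 (0.0087 × 150), against a half-width of 7.3 points. All of this stands, and it is why the point is minor. It does not remove the gap, which is systematic where the interval reflects chance. SAP 8.8.5 also governs the parent cohort of up to 650 subjects, where the half-width at R = 30% falls to 1.96 × sqrt(0.21/650) = 3.5 points and the gap does not fall.

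Third, deaths are listed, counted in disposition and included in the composite, so a reader can bound the effect. That also stands, but the published estimate and interval remain uncorrected.

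**Conclusion.** The concern holds, as a minor point confined to one-year readmission. The direction is certain from the plan's own rules: the Kaplan-Meier figure cannot fall below the cumulative incidence. The size cannot be fixed from the documents. Under the assumed ranges and constant hazards it is 0.1 to 2.6 points, and up to 4.4 points at the most extreme assumed rates if all deaths precede all readmissions. Each of these is smaller than the 95% half-width at 150 subjects. No test, threshold, primary endpoint or secondary endpoint is affected.

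**What to change.** In SAP 8.8.5, with a matching sentence in 9.5, state that one-year readmission is the Aalen-Johansen cumulative incidence of first readmission at 365 days, with death without prior readmission as the competing event. Replace Greenwood for this endpoint with a 95% interval from the delta-method (Aalen-type) variance of the cumulative incidence, on the log(-log) scale. The same estimator could be used at 30 days for consistency, but that is optional. Leave the Kaplan-Meier and Greenwood rule in SAP 8.2 unchanged for the death-or-stroke composite, where death is itself an event.

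The cost is a short SAP edit and a standard procedure call; death dates are already collected for the composite. Because SAP 8.8.5 also governs the parent study, the edit changes that analysis too. The one drawback is slightly less direct comparability with earlier Kaplan-Meier reports, including any parent-study interim report. A supportive Kaplan-Meier line, labelled as censoring death, would cover it.
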